4.3 Analysis of the primary objective

In order to assess the level to which participants incorporate the advice into their final estimates of the probability of survival, the WOA is calculated for each participant for each vignette(s). This is done by comparing their final estimate against the initial estimate and the advice provided. The final

estimate of probability of surviving two weeks can be represented as a weighted combination of the participant's initial estimate and the advice received, with the weights being proportional to the extent of the shift towards (away from) the advice. WOA will be defined as $= |f - i|/|a - i|$, where 'i', 'f', and 'a' stand for initial, final, and advice, respectively.

If a participant decides to adhere completely to his or her initial estimate (100% discounting of the advice), the weight of the advice will be 0. If the participant decides to shift completely to the advice then the weight of advice will be 1.0 (0% discounting). Intermediate weights indicate that positive weights were assigned to the initial estimate and the advice (partial discounting).

We will then use multilevel regression analysis accounting for multiple vignettes completed by each participant, to compare the means of the WOA scores for the two arms, the algorithm arm and the clinicians' arm.

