Statistical methodology and analysis:	
Analysis will be conducted by the study team. Participant demographics will be described.
 
The primary outcome will be the weighting of advice that each judge attributes to the advice that they receive. The weighting of advice reflects the importance that a judge gives to the advice provided and the level to which the judge incorporates this into their decision (ranging from '0' if completely discounting the advice to '1' if shifting completely to the advice). The weighting of advice will be analysed using regression analysis, taking into account the judge's initial and final estimates and the advice given. We will explore whether the weighting of advice is influenced by characteristics of (1) the advisor (a clinician or algorithm); (2) the judge (e.g. seniority); and (3) the advice itself (e.g. distance from judge's initial estimate).

--	--

7 Background and Rationale

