The table below summarises the risks and mitigations of all study procedures:

Intervention	Potential risk	Risk Management
Completion of an online experimental task to provide five prognostic estimates and receive prognostic advice from an 'advisor'	There are no obvious risks associated with the completion of this task. However, predicting survival is a difficult task, therefore participants may experience some feelings of frustration.	Participants will be advised that they can withdraw from the study at any time and without giving a reason.
Collection of data, using a secure online platform.	There is a small risk that data could be lost or accessed by unauthorised personnel.	Data will be encrypted, backed up and stored securely on UCL computers.

9 Objectives

To understand how clinicians form intuitive judgements about the prognoses of palliative care patients after receiving advice perceived as coming from either a team member or an algorithm.

9.1 Primary objective:

To assess the level to which clinicians incorporate advice received from other clinicians or an algorithm into their estimates of the prognosis of palliative care patients.

9.2 Secondary objective:

To investigate the extent to which clinicians' integration of advice is influenced by the characteristics of the judge, the advisor or the advice itself.

10 Study design

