Clinicians will be invited to participate in the study as part of a (online) seminar on palliative care by the CI or through an invitation email sent to their hospice medical director (see section 12.3). Seminar participants will receive information about the study before the seminar and will be invited to complete the online questionnaire in preparation for the seminar. The CI will make it clear that delegates at the seminar are under no obligation to complete the questionnaire.

Participants will be provided with a link to the study website and will complete all assessments online. The website will provide information regarding the study and a link to a PIS. Participants will be asked to tick check boxes to indicate that they are giving informed consent. After filling in the demographics section, eligible participants will be considered to be enrolled and a participant ID will be assigned. Next, participants will be randomly allocated to one of the two study groups. This will be performed through the web-based system, using a pre-generated blocked randomisation list.

Participants will be given tailored instructions, shown a practice vignette and will then be able to start the decision tasks and to provide estimates of the probability of patients surviving two weeks. Participants will be presented with five vignettes. Vignettes will be presented in random order to prevent order effects.

There will be no time limit for completion, so that each participant will be able to consider their responses. Participants will be given the opportunity to log out and return to the same place at a more convenient time. Participants will not be able to move on to the next page if required information is missing or is in an incorrect format (e.g. incorrect email format). The online environment will be piloted by the study team in close collaboration with the study statistician who will review the data being collected before, during, and at the start of the recruitment phase to ensure data integrity.

After completing the series of vignettes, participants will be shown a debrief page to remind the participant what the results will be used for and they will be able to download a certificate of participation. Participants will be asked if they wish to receive a summary of the results at the end of the study and whether they would be willing to be approached for subsequent studies.

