60%	Reduced	Unable hobby/house work Significant disease	Occasional assistance necessary	Normal or reduced	Full or Confusion
50%	Mainly Sit/Lie	Unable to do any work Extensive disease	Considerable assistance required	Normal or reduced	Full or Confusion
40%	Mainly in Bed	Unable to do most activity Extensive disease	Mainly assistance	Normal or reduced	Full or Drowsy +/- Confusion
30%	Totally Bed Bound	Unable to do any activity Extensive disease	Total Care	Normal or reduced	Full or Drowsy +/- Confusion
20%	Totally Bed Bound	Unable to do any activity Extensive disease	Total Care	Minimal to sips	Full or Drowsy +/- Confusion
10%	Totally Bed Bound	Unable to do any activity Extensive disease	Total Care	Mouth care only	Drowsy or Coma +/- Confusion
0%	Death	-	-	-	-

What do you think the probability is that this patient will survive the next two weeks?

.....%

Please write your answer as a percentage in the box to the right

(Scale: 0-100. Where 0% means certain to die and 100% means certain to survive)

FOR THE CLINICIAN ADVICE:

A palliative care [nurse/doctor] estimated (based on the provided patient information) that the probability this patient will survive the next two weeks was:

.....%

FOR THE ALGORITHM ADVICE:

The PiPS-B14 estimated (based on the provided patient information) that the probability this patient will survive the next two weeks was:

.....%

What is your final estimate of the probability this patient will survive the next two weeks?

.....%

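### The primary measure, WOA = |f − i|/|a − i|, scores a move away from the advice as uptake and can exceed 1, against the plan's own 0–1 reading

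*SAP*

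**What the plan says.** SAP 4.3 gives the formula: "WOA will be defined as $= |f - i|/|a - i", the numerator and denominator both being absolute differences. Protocol 16.2.2 has the same formula. Both sections first describe the final estimate as a weighted average of the initial estimate and the advice, "with the weights being proportional to the extent of the shift towards (away from) the advice". They then fix the meaning of the scale. At the lower end, for a participant who chooses to "adhere completely to his or her initial estimate (100% discounting of the advice), the weight of the advice will be 0". At the upper end, "If the participant decides to shift completely to the advice then the weight of advice will be 1.0 (0% discounting". Values in between are read as partial discounting. The Protocol summary (section 6) states the range outright: "ranging from '0' if completely discounting the advice to '1' if shifting completely to the advice".

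Mean WOA is what the two randomised groups are compared on (SAP 4.3). The primary objective is also about level: "To assess the level to which clinicians incorporate advice received from other clinicians or an algorithm" (Protocol 9.1).

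**The concern.** The formula drops the sign that the surrounding text relies on. A participant who reacts against the advice gets the same positive score as one who moves towards it by the same amount. Nothing limits the score at 1, so a small gap between initial estimate and advice can give a very large value.

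Two results are exposed. The reported level of uptake is too high whenever anyone moves away from the advice, whatever the group. The comparison of algorithm-labelled with clinician-labelled advice is distorted if moves away differ between the groups. Rejecting advice because of its label is one of the behaviours this comparison could reveal, and the formula would record it as acceptance.

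**Working it through.** **What the plan's own description implies.** If the final estimate is a weighted average, f = w·a + (1 − w)·i. Solving for w gives w = (f − i)/(a − i), which is signed. This equals the plan's formula when f lies between i and a, and also when f goes past a. It differs in sign when f is on the far side of i from a. Take i = 60, a = 75, f = 45. The plan's formula gives 15/15 = 1. Putting w = 1 back into the weighted average returns 75, not 45. The signed value, −1, returns −75 + 120 = 45.

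**Worked scores.**

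| i | a | f | Move | Plan's formula | Signed | Signed, restricted to 0–1 |
|---|---|---|---|---|---|---|
| 60 | 90 | 60 | none | 0 | 0 | 0 |
| 60 | 90 | 75 | towards | 0.5 | 0.5 | 0.5 |
| 60 | 90 | 90 | full | 1 | 1 | 1 |
| 60 | 90 | 45 | away | 0.5 | −0.5 | 0 |
| 60 | 75 | 45 | away | 1 | −1 | 0 |
| 85 | 90 | 75 | away | 2 | −2 | 0 |
| 85 | 90 | 95 | past the advice | 2 | 2 | 1 |
| 75 | 76 | 80 | past the advice | 5 | 5 | 1 |

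The first three rows reproduce the plan's anchors. The last two show that a sign alone does not remove values above 1, so a second rule is needed for overshoot.

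**Can these answers occur?** SAP 3.2.1 puts both estimates on a 0–100% scale. The sample form in Protocol Appendix 2 asks "What is your final estimate of the probability this patient will survive the next two weeks" with a blank to fill in. The entry check in Protocol 11 is that "Participants will not be able to move on to the next page if required information is missing or is in an incorrect format", which does not concern direction. Exclusions (Protocol 12.5 and 16.2, SAP 2.2 and 4.2) cover incomplete sets and non-compliance such as identical or hurried answers. As an outer bound only, whole-number answers with advice at 90, 75 and 50 (the values the plan mentions) allow WOA up to 91 (i = 91, f = 0), 76 (i = 76, f = 0) and 51 (i = 51, f = 0).

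**Effect on the level.** Let a share q of responses move away with size |w|. Each counts +|w| under the plan, −|w| under the signed form and 0 under the restricted form. The mean is therefore too high by 2q|w| and q|w| respectively. With q = 5% and |w| = 1 (assumed), that is 0.10 and 0.05.

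**Effect on the group difference.** If the shares moving away differ by d between groups at the same |w|, the difference is off by 2d|w| against the signed form and d|w| against the restricted form. It is off by zero if the groups are equal.

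**Scale for comparison.** The full 95% CI width in Protocol 16.1, Table 1, is 2 × 1.96 × SD × √(4/n), with n the total and equal groups (equal allocation is inferred because it reproduces the table). For n = 100 this gives 0.235 (SD 0.3) and 0.314 (SD 0.4); for n = 200, 0.166 and 0.222. The table prints 0.24, 0.31, 0.17 and 0.22. The half-width therefore runs from 1.96 × 0.3 × √(4/200) = 0.083 to 1.96 × 0.4 × √(4/100) = 0.157.

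Difference d in shares moving away that shifts the group comparison by one half-width:

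| Size of move | Against signed, half-width/(2·size) | Against restricted, half-width/size |
|---|---|---|
| 1 | 4.2% to 7.8% | 8.3% to 15.7% |
| 0.5 | 8.3% to 15.7% | 16.6% to 31.4% |

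**A real effect can also be hidden.** Suppose everyone in one group moves 0.5 towards the advice, while in the other a share p moves 0.5 away and the rest 0.5 towards. The plan's formula reports a difference of 0 for any p. The signed difference is 0.5 − [0.5(1 − p) − 0.5p] = p.

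**The case against.** The algebra is not in dispute; the case on the other side is about how much it matters.

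- Protocol 7.4 reports that people revising an estimate usually choose one of the two values or average them. Either way f stays between i and a, where the formula is correct. This is fair for typical answers, but it describes a tendency, and SAP 4.3 itself mentions shifts away.
- Both groups see the same advice and are randomised. If the label has no effect, unsigned WOA has the same distribution in both groups and false positives do not rise. This stands. It protects the test under the null, but neither the reported level nor the estimate when the label does change behaviour.
- Values above 1 through overshoot come from a missing limit, not from the absolute values. This also stands, and the two faults need separate rules.
- The plan names three advice values for five vignettes, and the sample form may differ from the final one. So 91, 76 and 51 are not limits for the actual trial, and the form is only supporting evidence. The 0–100% scale in SAP 3.2.1 is firmer.
- Protocol 16.2.2 cites a published source for the formula. Whatever that source does with answers outside the interval, neither document states a rule.

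**Conclusion.** The definition is wrong as written and must be corrected before analysis. For any move away from the advice, the formula gives a score that contradicts the weighted average and the anchors in the same section. Values above 1 contradict the range in the Protocol summary. This is algebra and needs no assumption about behaviour.

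The size of the effect on results is unknown, because the documents give no frequency of such answers; the shares and move sizes used above are assumptions. The group difference is unaffected if moves away are equally frequent and equally large in both groups. The severity rests on the primary measure not meaning what the plan says it means, and on the fact that choosing a sign or limit after seeing the data would be a post-hoc choice on the primary result.

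Separately, WOA is undefined when a = i and no rule is given. This is a minor omission: Stata, named in SAP 5, would return a missing value and drop that row.

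**What to change.** In SAP 4.3 and Protocol 16.2.2:

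1. Define WOA = (f − i)/(a − i), with sign.
2. State one rule for values outside 0–1 in the primary analysis, for example restricting them to 0–1. Which version is primary is a judgement, but it must be fixed in advance.
3. If values are restricted, analyse the unrestricted signed version as a sensitivity analysis, because restriction scores a move away the same as ignoring the advice.
4. Report by randomised group how many values fall below 0 and above 1.
5. State that when a = i only that vignette is dropped, that the participant stays in the analysis, and that the count is reported by group.

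The cost is a few lines of text and code, with no new data. Restricting hides how extreme some answers are; the counts and the sensitivity analysis disclose it.

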4.4 Analysis of the secondary objective

We will perform regression analyses to explore any associations between participants' weighting policies and characteristics of the participants (profession, gender, age, work environment etc.).

We want to explore any associations between participants' weighting policies and the advice itself (e.g. the strength of the advice) as well. Participants will receive five pieces of advice from the PiPS data. They will receive advice given with high confidence (i.e. the patient has 90% probability of surviving the next 14 days), with lower confidence (i.e. 75% probability of survival) and one where the advice is equivocal (i.e. 50% probability of survival).

Multilevel regression analyses will be used to take into account multiple vignettes are completed by each participant.

5 General statistical considerations

All the statistical summaries and analysis will be performed using Stata version 15 (or above).

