Study data will be collected using two different recruitment methods (arm A and arm B). Both study arms involve participants being asked to provide a prognostic estimate of the probability of survival for palliative care patients. Participants are asked to provide information about their gender, age, role, grade and experience. They will be presented with five case summaries ("vignettes") (see Appendix 2 – Sample vignette) based on real cases derived from a previous study (PiPS2) (Kalpakidou et al., 2018). In the PiPS2 study, data were collected on palliative care patients in order to calculate a prognostic score (the PiPS score). Doctors and nurses were asked to make a prediction about how long they expected the patient to survive, and the subsequent length of survival of the patients was recorded. We will create vignettes using the anonymised data already collected as part of the PiPS2 study (see Appendix 2 – Sample vignette). Participants will be presented with key prognostic information and will be asked to estimate the probability that the patient will survive the next two weeks (0% 'certain to die' to 100% 'certain survival').

Participants will be randomised into one of the following two groups: The clinicians' advice group or the algorithm advice group. In the clinicians' advice group, participants will receive advice labelled as coming from another clinician. Doctors will receive advice labelled as coming from nurses and *vice versa*. Seminar attendees with other clinical backgrounds in this group will be further randomised into receiving advice labelled as either coming from a doctor or a nurse. In the algorithm group, participants will receive advice labelled as coming from the PiPS-B algorithm. In fact, participants in both groups will receive the same advice. After receiving the advice, participants will be given the opportunity to give a revised estimate, in the light of the advice received.

A schedule of study assessments and procedures is set-out in Appendix 1 - Schedule of assessments.

11 Data collection and study procedures

We expect that data collection for this study will take approximately ten months starting in August 2020 and end by April 2021. See the Gantt chart in the appendix.

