16.1 Sample size calculation

We aim at recruiting between 100-200 clinicians within the 10 month time period of recruitment (August 2020-April 2021). This will be sufficient to address the objectives of the study. We will stop recruiting and close down the website when we have accrued 300 respondents with complete data within the recruitment period (before April 2021).

We want to compare the means of the weighting of advice (WOA) of the two groups, (the group receiving advice labelled as coming from an algorithm and the group receiving advice labelled as coming from a clinician), with a confidence interval (CI) of 95%. Based on calculations from a similar study by Logg et al. (2019) we expect the standard deviation (SD) to be between 0.3 and 0.4. This will give a width of the CI between 0.17 and 0.31, depending on the sample size and the SD (see the table below). These numbers are based on and calculated from the guidelines by Machin et al. (2018). This means that a sample size between 100-200 respondents should be sufficient to detect a significant difference between the mean WOAs of the two groups if the mean difference is greater than 0.085 to 0.22.

Table 1: The width of the confidence interval varying by sample size and SDs

Sample Size	Expected SD for mean diff in WOA	
	$\sigma = 0.3$	$\sigma = 0.4$
50	0.33	0.44
100	0.24	0.31
150	0.19	0.26
200	0.17	0.22
250	0.15	0.20
300	0.14	0.18

The calculations above are sufficient to address the primary objective of the study which is to assess the level to which clinicians incorporate advice received from other clinicians or an algorithm into their estimates of the prognosis of palliative care patients.

The online survey consists of five vignettes. Increasing the number of vignettes would increase generalisability of the study but would add to the study burden for the participants and increase the risk that the study would not be completed by respondents. It was considered that five vignettes was a suitable balance between generalisability and study burden.

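### Advice strength is tied to the vignette and its equivocal level is a single case, so SAP 4.4 cannot separate strength from case content, and it names no vignette term for predictors that vary within a case

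*SAP*

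**What the plan says.** The secondary objective includes the influence of the advice on its own uptake. SAP 4.4 puts it this way: "We want to explore any associations between participants' weighting policies and the advice itself", with strength as the example. It lists five pieces of advice: some at high confidence, some at lower confidence, and "one where the advice is equivocal (i.e. 50% probability of survival"). The modelling instruction is "Multilevel regression analyses will be used to take into account multiple vignettes are completed by each participant". No vignette effect, fixed or random, is named in SAP 4.3, SAP 4.4 or Protocol 16.2, and none is ruled out.

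The Protocol summary (section 6) gives another example of an advice characteristic: "the advice itself (e.g. distance from judge's initial estimate"). SAP 4.4 does not list distance.

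On how advice is assigned, Protocol section 10 says of the two randomised groups: "In fact, participants in both groups will receive the same advice". The sample vignette in Protocol Appendix 2 presents the advice as an estimate for the patient just described: "The PiPS-B14 estimated (based on the provided patient information"). Protocol section 11 randomises the order of the vignettes. SAP 4.2 drops anyone who does not complete all five.

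On the number of cases, Protocol 16.1 says: "It was considered that five vignettes was a suitable balance between generalisability and study burden".

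**The concern.** If every participant sees the same five patients, and each patient comes with one advice value, strength is a label on the patient. Suppose the equivocal advice is followed less than the rest. The cause may be that it was equivocal, or something else about that one patient summary. Random order balances position effects, not case content. Clustering by participant deals with repeated answers from one clinician and does nothing about this.

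Distance is different, because clinicians start from different initial estimates for the same patient. But average distance will also differ between patients. Without a vignette term, the distance coefficient mixes the within-case relation with differences between cases.

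At stake is the interpretation of part of the secondary objective: features of one patient could be published as an effect of advice strength, and case differences as an effect of distance.

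**Working it through.** **1. The plan's own figure.** Protocol Table 1 is the width of the 95% CI for the difference between groups, 2 × 1.96 × SD × √(4/N). For N = 100 this gives 0.235 (SD 0.3) and 0.314 (SD 0.4), against 0.24 and 0.31 printed. For N = 200 it gives 0.166 and 0.222, against 0.17 and 0.22. All 12 cells agree to rounding. The formula uses one value per participant. So where Protocol 16.1 says "we expect the standard deviation (SD) to be between 0.3 and 0.4", the SD could be (a) that of a clinician's mean over vignettes or (b) that of a single response. Both are carried below.

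**2. Confounding of strength with case (no numerical assumption).** Inputs: five vignettes, one advice value each, one equivocal. Five vignette indicators have rank 5. Adding strength leaves the rank at 5 for high/lower/equivocal splits of 2/2/1, 3/1/1 and 1/3/1, and also when strength is a linear score. Vignette fixed effects therefore absorb strength completely. With vignette as a random effect, strength can formally be estimated, but on 5 − 3 = 2 df for three levels (critical t 4.30) or 5 − 2 = 3 df for a linear score (3.18). This holds whatever the number of participants, and only if case effects are exchangeable.

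**3. Illustration: reading a strength contrast beyond these five cases.** Assumed: SD 0.35, intraclass correlation (ICC) 0.4, between-vignette SD τ. The ratio of true to participant-clustered standard error for any single contrast of vignette means is r = √(1 + Nτ²/s²), and the type I error is 2 × (1 − Φ(1.96/r)).

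- Reading (a): per-response variance 0.35²/(0.4 + 0.6/5) = 0.236, so s = √(0.236 × 0.6) = 0.376.
- Reading (b): s = 0.35 × √0.6 = 0.271.
- Example, (b), N = 200, τ = 0.02: r = √(1 + 200 × 0.0004/0.0735) = 1.445, error 17.5%.

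| τ | (a) N = 100/200/300 | (b) N = 100/200/300 |
|---|---|---|
| 0 | 5/5/5% | 5/5/5% |
| 0.02 | 8/12/15% | 12/18/23% |
| 0.05 | 24/36/43% | 35/48/56% |

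Over both readings, from SD 0.4 with ICC 0.2 to SD 0.3 with ICC 0.6, the range is 6–35% at τ = 0.02 and 13–67% at τ = 0.05.

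**4. Illustration: distance.** Simulated with no true distance effect, WOA generated independently of distance, N = 200, SD of distance 15 points within vignettes and 5/10/15 points between them (all assumed). Without a vignette term, false positives are (a) 6/6/8% and (b) 7/8/11% at τ = 0.02, and (a) 11/18/21% and (b) 13/23/33% at τ = 0.05. With vignette fixed effects they are 4–6%.

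**5. What step 4 leaves out.** SAP 4.3 defines WOA as |f − i|/|a − i|, so distance is the denominator of the outcome. A clinician who gives the advice no weight but whose final answer drifts by 2 points scores 2/5 = 0.40 at a distance of 5 points and 2/25 = 0.08 at a distance of 25. When WOA is simulated from its definition, with true weight independent of distance and vignette fixed effects fitted, false positives are about 4–6% with no response noise. They are 47–100% with an assumed 1–2 points of noise in the final estimate. The size depends on those assumptions; the mechanism follows from the formula.

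**The case against.** The strongest reply is that the plan claims little. SAP section 4 calls the analysis mainly descriptive, SAP 4.4 speaks of exploring associations, and neither document specifies a strength test, a contrast or a claim beyond these cases. Intervals clustered by participant are valid for differences among the five cases actually shown. This stands. A reader might infer from step 3 that the plan has a false-positive rate of up to two thirds. The documents do not support that: those rates belong to a generalising reading that the plan does not state, and they rest on values of τ and ICC that it does not give.

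Second, fixed advice per vignette is inferred. The statement in Protocol section 10 compares the two groups, not participants within a group. This also stands, though nothing in either document suggests that advice varies within a case.

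Third, inseparability is exact only for the equivocal level and for models with vignette fixed effects. High and lower confidence share the other four cases in an unstated split. That is right, but the random-effects route offers 2–3 df and needs an assumption about the cases that five cannot test.

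Fourth, Protocol 16.1 already accepts limited generalisability. That remark weighs the number of vignettes against burden. It does not tell the reader that strength and case are the same variable here.

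Fifth, SAP 4.4 does not list distance, and a vignette term is not excluded. Both are true, so this part asks for a specification and does not correct an error. A reader might also infer that a vignette term makes a distance coefficient sound; step 5 shows that it does not.

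**Conclusion.** The concern holds in limited form. Given one advice value per vignette, strength as planned in SAP 4.4 cannot be separated from case content at any sample size, and no caveat says so. For predictors that vary within a vignette, a model clustered by participant alone also picks up differences between cases. The confounding rests only on the inference about fixed advice. The percentages rest on an assumed between-vignette SD, ICC and spread of distance; at τ = 0 there is no inflation, so they show a possible range and not the study's error rate.

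A reader might extend the concern to the primary analysis. The documents do not support this: both randomised groups see the same five cases with the same advice, so case content does not differ between the algorithm and clinician groups. This is a low-cost clarification of an exploratory analysis, worth making before results are interpreted.

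**What to change.** In SAP 4.4:

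1. Report mean WOA with a 95% CI for each of the five vignettes, labelled by its advice value. State that differences between strengths describe these five cases and cannot be attributed to strength rather than case content.
2. Include vignette as a fixed effect in models for predictors that vary within a vignette.
3. State that item 2 removes between-case confounding only. Because |a − i| is also the denominator of WOA, response noise can create a distance association even with vignette effects, so a distance coefficient should be reported as descriptive.

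Cost: a few sentences and a five-row table, with no change to data collection. No general effect of advice strength can be claimed. Under the assumptions of step 4 (ICC 0.4, N = 200), the interval for distance becomes about 1.07/1.23/1.46 times as wide at a between-vignette SD of distance of 5/10/15 points. With SD 0.35 and ICC 0.4, the half-width for one vignette mean at N = 100/200/300 is about 0.095/0.067/0.055 on reading (a) and 0.069/0.049/0.040 on reading (b).
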